### **5.2.2. Adverse Events**

All patients will be monitored carefully during and after the treatment courses of BI 6727. During the trial, all adverse events (AE) will be recorded in the eCRF as described in section 8.4 of this protocol. The events will be graded according to the CTCAE v3.0 (attached to the ISF).

Adverse events with onset within 21 days after the previous administration of therapy with BI 6727 are considered as on treatment. Adverse events which are not yet recovered at the end of treatment (EOT) visit will be followed up until recovery or in case of persistence sufficient characterisation of the toxic effects has been achieved and the investigator and the clinical monitor agree to not further pursue them. Adverse events occurring during the follow-up period after the EOT visit will be reported in case they are serious or considered drug-related by the investigator.

Hospitalisations for administrative reasons or hospitalisations already planned prior to informed consent need not be reported as an SAE. Progressive disease (PD) will not be reported as an SAE if it is considered the natural course of the disease but will be recorded in the eCRF. Disease progression will be analyzed as part of the efficacy evaluation. Pre-existing conditions at baseline other than the disease will be not recorded as Adverse Events if they remain unchanged during the trial.

### 5.2.3. Physical examination, height, body weight, performance status and electrocardiogram

A general physical examination will be performed at screening and at the end of the treatment. The same investigator should perform this examination. Physical examination will include measurement of height and of body weight and the evaluation of the ECOG performance score. Height will be documented only once at screening of course 1. Weight and ECOG score will also be assessed when BI 6727 treatment is started and at the end of the treatment. ECOG will also be assessed at the last visit of each course.

12-lead resting electrocardiograms (ECG) will be performed at baseline, at visit 2 before and at the end of BI 6727 infusion and at the last visit of each course. In patients eligible for repeated courses of treatment ECGs should be done at visit 2 of the third course (second repeated course) before and at the end of infusion of BI 6727, at the last visit of that course and whenever the investigator deems necessary. In case of drug related ECG changes additional ECG monitoring will be performed in the respective and later courses of treatment. Except for the screening ECG all ECGs have to be digitally recorded using dedicated equipment provided by a CRO [REDACTED]. ECG recordings will be done at the following time points:

- One ECG during the screening examination (no digital monitoring needed)
- On day 1 a series of three consecutive ECGs prior to start of infusion of BI 6727 (approx. experimental time -0:15 min)
- On day 1 a series of three consecutive ECGs after end of infusion of BI 6727 (approx. experimental time 1h 15 min)
- On day 1 of course 3 a series of three consecutive ECGs prior to start of infusion of BI 6727 (approx. experimental time -0:15 min)
- On day 1 of course 3 a series of three consecutive ECGs after end of infusion of BI 6727 (approx. experimental time 1h 15 min)
- At the visit 8 of the first course and visit 5 of the third course a series of three consecutive ECGs

The recordings will be checked for pathological results (to be recorded as AEs) by the investigator. In addition a centralised evaluation of all 12-lead ECGs recorded during day 1 of courses 1 and 3, visit 8 of course 1 and visit 5 of course 3 will be performed by a CRO [REDACTED]. This analysis will include the determination RR-intervals, PR-intervals, QRS-intervals, QT-intervals. The CRO is also in charge of a safety overread of ECGs (one ECG out of every series of three) which will be done by a board-certified cardiologist. To allow for a heart rate correction of QT intervals according to Fridericia's formula ( $QTcF = QT/RR^{-1/3}$ ) or other methods the QT intervals will be matched to the preceding RR intervals.

Physical examination will be performed prior to each course.

#### 5.2.4. Vital signs

Vital signs (blood pressure (BP) and pulse rate after 2 minutes supine rest) will be recorded at the screening visit and at the following time points: pre-infusion and 20 ( $\pm 5$ ), 65 ( $\pm 10$ ), 120 ( $\pm 30$ ) and 240 ( $\pm 30$ ) minutes after start of infusion of BI 6727, at every visit of the observation phase and at EOT.

#### 5.2.5. Laboratory examinations

Blood samples will be collected from venous blood at the times indicated in the flow chart.

Laboratory tests will include the following safety lab parameters:

- haematology

red blood cell count (RBC), haemoglobin, haematocrit, medium corpuscular volume (MCV), white blood cell count (WBC) and differential, platelets

- biochemistry

glucose, sodium, potassium, calcium, creatinine, aspartate amino transferase (AST), alanine amino transferase (ALT), alkaline phosphatase, lactate dehydrogenase (LDH), bilirubin, urea, serum protein electrophoresis (total protein, albumine,  $\alpha 1$ -globulines,  $\alpha 2$ -globulines,  $\beta$ -globulines,  $\gamma$ -globulines), uric acid, creatine phosphokinase (CPK). In case of pathological CPK further evaluation (e.g. by Troponin assays) should be performed and the findings documented.

- coagulation parameters

prothrombin time (PT), international normalised ratio (INR) where therapeutically indicated and partial thromboplastin time (PTT) (at day 1 before start of infusion and at day 2)

- tumour markers

in applicable tumour types markers will be taken at screening and at visit 8 (visit 5 of repeated courses) e.g.: PSA, AFP,  $\beta$ -HGG, CA 125, CEA, CA 19-9, NSE, TPA, CA 15.3, CYFRA 21-1, chromogranine, thyreoglobuline.

These parameters will be assessed as specified in the flow chart. In case of toxicity adequate and more frequent blood sampling is at the discretion of the investigator. In case of grade 4 neutropenia, blood has to be collected seven days after first occurrence of grade 4 neutropenia.

In case laboratory investigations have been performed within two weeks prior to screening, these values may be used for screening and no repeat laboratory examination is requested for the purpose of the trial.

- Urine (pH, glucose, erythrocytes, leukocytes, protein, nitrite) will be analysed by dipstick (semiquantitative measurements; -, +, ++, +++) during the screening visit, at visit 3 of initial

treatment course, at visit 1 and 2 of repeated treatment courses and at the end of treatment visit. In case of pathological findings, further evaluation should be performed and the findings documented. A pregnancy test will be performed at screening and immediately before any further administration of BI 6727 in women of childbearing potential.

### **5.2.6. Significant adverse events**

Reaching DLT has to be recorded as a significant adverse event.

## **5.3 OTHER**

### **5.3.1. Demographics and history**

Demographics (sex, birth date, race), information on smoking and alcohol status, and baseline conditions will be collected during the screening visit and updated information will be collected at the first visit of additional courses.

History of cancer will also be obtained. The type of cancer, the date of first histological diagnosis (month and year may be sufficient), and the primary tumour site will be reported into the eCRF. The differentiation grade (not specified, poorly differentiated, moderately differentiated, well differentiated), the number and location of metastatic sites as well as the stage according to the tumour, (lymph) node, metastasis (TNM) classification and the Union Internationale Contre le Cancer (UICC) / American joint committee on cancers (AJCC) classification will be provided as obtained at diagnosis. It will also be recorded whether visceral involvement, bone involvement or soft tissue involvement is present (yes, no, unknown). Previous surgeries will be reported. Previously administered chemo-, immuno-, and hormone therapy will be reported including start and end dates (month and year may be sufficient), the therapy protocol with the number of courses (chemo-, immunotherapy), the best response obtained (complete response, partial response, stable disease, progressive disease, unknown) as well as whether the therapy was given as neoadjuvant, adjuvant, or palliative therapy. Concerning previous radiotherapy the total radiation dose and radiation field will be recorded.

### **5.3.2. Concomitant diagnoses and/or therapies**

Concomitant diagnoses and/or therapies present at study entry and/or during screening and relevant to the patient's safety during the trial as judged by the Investigator, will be recorded in the eCRF.

### **5.3.3. Genotyping for Pharmacokinetics**

One blood sample will be collected for cytochrome P 450 (CYP2D6, CYP2C19, CYP2C9) and N-acetyltransferase (NAT2) genotyping to evaluate the possible influence of their polymorphism on the pharmacokinetic profile of BI 6727.

In order to analyse the pharmacokinetic data in more detail, an investigation should help to clarify if different interindividual areas under the concentration time curves at same dosages might be explained by the respective genotypes. These results could help to elucidate the maximal tolerable dose.

To perform such analysis, EDTA-anticoagulated blood samples for DNA isolation will be collected once at visit 2 after separate informed consent.

Only testing for genes involved in drug metabolism will take place and that no polymorphisms of genes which might predispose for different diseases will be analysed. Only frequent functional polymorphisms will be analyzed.

#### **5.4 APPROPRIATENESS OF MEASUREMENTS**

Not applicable.

#### **5.5 DRUG CONCENTRATION MEASUREMENTS / PHARMACOKINETICS**

Date and exact clock time of administration (start and end time of infusion) as well as of pharmacokinetic sampling times must be recorded. These actual sampling times will be used for determination of pharmacokinetic parameters.

The designation “before”/“predose” on study day 1 refers to the time period of 0:05 before drug administration (see Appendix 10.2), i.e. study measurements and assessments scheduled to occur “before”/“predose” have to be performed and completed 0:05 prior to drug administration/start of infusion.

##### **5.5.1 Methods and timing of sample collection**

###### **5.5.1.1 Plasma sampling for pharmacokinetics**

A total amount of 42 mL blood will be taken per subject during the initial treatment course of the study for pharmacokinetic purposes. Subsequent courses will require 12 mL of blood for pharmacokinetic sampling. The samples need to be taken in the opposite arm, not in the infusion arm. For patients having central venous access, BI 6727 may be administered using this device and PK samples obtained from either forearm.

For quantification of analyte plasma concentrations, 3 mL of blood will be taken in an EDTA (ethylenediaminetetraacetic acid)-anticoagulant blood drawing tube at the following time points:

During the initial treatment course:

At visit 2 – day 1: before drug administration and at 0:15, 0:30, 0:45, 1:00\*, 1:30, 2:00, 4:00, 8:00 hours after start of infusion (\*immediately prior to end of infusion of BI 6727).

At visit 3 – day 2: 24:00 hours after start of infusion

At visit 4 – day 3: 48:00 hours after start of infusion

At visit 5 – day 5 ( $\pm 1$  day): planned time 96:00 hours after start of infusion

At visit 6 – day 8 ( $\pm 1$  day): planned time 168:00 hours after start of infusion

At visit 7 – day 15 ( $\pm 1$  day): planned time 336:00 hours after start of infusion

During additional courses plasma samples will be taken at the following time points:

At visit R1 – day 1: prior to the end of infusion (1:00)

At visit R2 – day 2: 24:00 after start of infusion

At visit R3 – day 8 ( $\pm 1$  day): planned time 168:00 hours after start of infusion

At visit R4 – day 15 ( $\pm 1$  day): planned time 336:00 hours after start of infusion

Until shipment on dry ice to the analytical laboratory, the plasma samples will be stored at  $-20^{\circ}\text{C}$  or below at the clinical site and stored at the analytical laboratory at  $-20^{\circ}\text{C}$  or below until analysis.

[figure not shown]
Detailed handling instructions for plasma samples are provided in Appendix 10.3.

[figure not shown]
#### 5.5.1.2 Urine sampling for pharmacokinetics (in course 1 only)

A blank urine sample will be collected prior to drug administration and two 2 mL aliquots retained to check for analytical interference. A protocol start time of -2:00 and a stop time of -2:00 will be used for database setup. All urine voided during the sampling intervals 0-24 and 24-48 hours after administration will be collected in containers. Patients have to empty their bladder at the end of each sampling interval. The urine weight/volume (weight will be set equal to volume, i.e. 1 kg = 1 L, without correction for specific gravity of urine) for each collection interval will be documented (the weight of the empty and the filled container needs to be documented) and two 2 mL aliquots will be stored for bioanalytical measurement.

Until shipment on dry ice to the analytical laboratory, the urine samples will be stored at  $-20^{\circ}\text{C}$  or below at the clinical site and stored at the analytical laboratory at  $-20^{\circ}\text{C}$  or below until analysis.

Detailed handling instructions for urine samples are provided in Appendix 10.3.

[figure not shown]

## **5.6 BIOMARKER / PHARMACODYNAMIC SAMPLING**

### **5.6.1 Methods and timing of sample collection**

In applicable tumour types markers will be taken at screening and at visit 8 (visit 5 of repeated courses) e.g.: PSA, AFP,  $\beta$ -HGG, CA 125, CEA, CA 19-9, NSE, TPA, CA 15.3, CYFRA 21-1, chromogranine, thyreoglobuline. (c.f. 5.2.6).

## **5.7 PHARMACOKINETIC / PHARMACODYNAMIC RELATIONSHIP**

No analysis of pharmacokinetic/pharmacodynamic relationship is planned.

## **5.8 DATA QUALITY ASSURANCE**

A quality assurance audit of this trial may be conducted by the sponsor or sponsor's designees. The quality assurance auditor will have access to all medical records, the investigator's trial related files and correspondence, and the informant consent documentation that is relevant to this clinical trial.

## 6. INVESTIGATIONAL PLAN

This is an open label, uncontrolled trial in patients with various solid tumours following the 3+3 design with dose escalation (R04-0569). The aim is to assess the MTD of BI 6727 administered at escalating doses.

Patients meeting the inclusion and exclusion criteria and who have given their written informed consent are eligible for participation in the trial.

Three to six patients each will be administered BI 6727 at a certain dose level. For exact dosing details refer to section 4.1.3.1. A total of 24 patients will be treated at the MTD.

### 6.1 VISIT SCHEDULE

#### 6.1.1. Visit schedule in initial treatment course

##### 6.1.1.1. Visit 1 – screening visit

The screening visit has to be performed within day -14 and the day before first administration of BI 6727.

##### 6.1.1.2. Visit 2 – day 1

Visit 2 is the day of administration of BI 6727.

##### 6.1.1.3. Visit 3 – day 2

Visit 3 is the day after the first administration of BI 6727.

##### 6.1.1.4. Visit 4 – day 3, visit 5 – day 5 ( $\pm 1$ ), visit 6 – day 8 ( $\pm 1$ ) and visit 7 – day 15( $\pm 1$ )

Visits 4 through 7 should be performed on days 3, 5 ( $\pm 1$ ), 8 ( $\pm 1$ ) and 15 ( $\pm 1$ ).

##### 6.1.1.5. Visit 8 – day 22 ( $\pm 2$ )

Visit 8 should be performed on day 22 ( $\pm 2$ ).

#### 6.1.2. Visit schedule in repeated treatment courses

##### 6.1.2.1. Visit 1 – day 1

Visit 1 is the day of administration of BI 6727.

##### 6.1.2.2. Visit 2 – day 2

Visit 2 is the day after the first administration of BI 6727.

6.1.2.3. Visit 3 – day 8 ( $\pm 1$ ), visit 4 – day 15 ( $\pm 1$ )  
and visit 5 – day 22 ( $\pm 2$ )

Visits 4 through 5 should be performed on days 8 ( $\pm 1$ ); 15 ( $\pm 1$ ) and 22 ( $\pm 2$ )

## **6.2 TRIAL PROCEDURES AT EACH VISIT**

### **6.2.1 Screening phase**

Visit 1 – Screening visit (day -14 to day 0)

- informed consent
- demographics (sex, birth date, race)
- history (oncological and relevant non oncological)
- patient eligibility (in- and exclusion criteria)
- physical examination including resting ECG, body weight, height, vital signs (blood pressure, pulse rate) and ECOG performance score
- pregnancy test in women of childbearing potential
- concomitant therapy
- Endosonography or ultrasound of primary or metastatic marker lesions (optional)
- tumour assessment. MRI and CT scans should not be older than 4 weeks
- tumour markers (in applicable tumour types of the underlying disease)
- laboratory examination including safety lab parameters (haematology including differential, biochemistry, coagulation parameters), urine dipstick

### **6.2.2 Treatment phase(s)**

6.2.2.1. Treatment phase in course 1

Visit 2 – day 1

Visit 2 – day 1, day of BI 6727 administration

- patient eligibility (in- and exclusion criteria)
- final confirmation of dose tier
- changes in concomitant therapies

- occurrence of adverse events (AEs) since enrolment
- body weight
- ECOG performance score
- blood sampling for cytochrome P450 (CYP2D6, CYP2C19, CYP2C9) and NAT2 genotyping

immediately before administration of BI 6727:

- resting ECG (series of three consecutive ECGs using dedicated equipment)
- vital signs (blood pressure, pulse rate)
- safety lab parameters (haematology including differential, biochemistry)
- Pharmacokinetic blood sampling: obtain predose blood sample (-0:05) (refer section 10.3 for sample handling). The date and time of sampling must be recorded in the eCRF.
- Pharmacokinetic urine sampling: obtain predose urine sample (at least two 4 mL aliquots)

following administration of BI 6727 (start of infusion: 0:00) (the infusion rate needs to be constant during the whole infusion, deviations need to be documented in the eCRF. Duration (start and stop time of infusion) and actual dose administered need to be documented):

- vital signs (blood pressure, pulse rate) at 20 ( $\pm$  5 minutes), 65 ( $\pm$  10 minutes), 120 (2 hours;  $\pm$  30 minutes) and 240 minutes (4 hours;  $\pm$  30 minutes) after start of infusion
- Pharmacokinetic blood sampling: obtain blood samples at the following time points: 0:15, 0:30, 0:45, 1:00 (immediately prior to end of infusion of BI 6727), 1:30, 2:00, 4:00, 8:00 h after start of infusion of BI 6727 (refer section 10.3 for sample handling). Blood samples have to be taken in the opposite arm of the infusion arm. For patients having central venous access, BI 6727 may be administered using this device and PK samples obtained from either forearm. The date and time of blood sampling must be recorded in the eCRF.
- Pharmacokinetic urine sampling: start urine sampling (0-24 h, only in first course)
- adverse events occurring during and after infusion
- changes in concomitant therapy
- resting ECG (series of three consecutive ECGs using dedicated equipment)

Visit 3 - day 2

- vital signs (blood pressure, pulse rate)
- Pharmacokinetic blood sampling: obtain blood sample 24:00 h after start of infusion of BI 6727 (refer section 10.3 for sample handling). The date and time of blood sampling must be recorded in the eCRF.
- Pharmacokinetic urine sampling: collect urine container from first interval and place new container for second interval to patients disposal (24-48 h, only in first course) (refer to section 10.3 for sample handling).
- adverse events
- changes in concomitant therapy
- safety lab including haematology, biochemistry, coagulation parameters
- urine dipstick

Visit 4 - day 3

- vital signs (blood pressure, pulse rate)
- adverse events
- changes in concomitant therapy
- safety lab including haematology, biochemistry
- Pharmacokinetic blood sampling: obtain blood sample 48:00 h after start of infusion of BI 6727 (refer to section 10.3 for sample handling). The date and time of blood sampling must be recorded in the eCRF.
- Pharmacokinetic urine sampling: collect urine container from second interval (24-48 h, only in first course) (refer section 10.3 for sample handling).

Visit 5 - day 5 ( $\pm 1$ )

- vital signs (blood pressure, pulse rate)
- adverse events
- changes in concomitant therapy
- safety lab including haematology, biochemistry

- Pharmacokinetic blood sampling: obtain blood sample 72:00, or 96:00, or 120:00 h after start of infusion of BI 6727 (respectively at day 4, or day 5, or day 6) (refer to section 10.3 for sample handling). The date and time of blood sampling must be recorded in the eCRF.

#### Visit 6 - day 8 ( $\pm 1$ ) and Visit 7 - day 15 ( $\pm 1$ )

- vital signs (blood pressure, pulse rate)
- adverse events
- changes in concomitant therapy
- safety lab including haematology, biochemistry
- Pharmacokinetic blood sampling: obtain blood sample at visit 6 (planned time: 168:00 hours after start of infusion of BI 6727) and at visit 7 (planned time: 336:00 hours after start of infusion), respectively (refer to section 10.3 for sample handling). The date and time of blood sampling must be recorded in the eCRF.

#### Visit 8 - day 22 ( $\pm 2$ )

Visit 8 is the last visit of the initial treatment course. This visit may coincide with day 1 of the following treatment course. Examinations which are due on both present visit and the day of BI 6727 administration need to be documented only once (in the day 22 visit).

- vital signs (blood pressure, pulse rate)
- ECOG performance score
- adverse events
- changes in concomitant therapy
- safety lab including haematology, biochemistry, coagulation parameters
- Endosonography or sonography (optional)
- resting ECG (series of three consecutive ECGs using dedicated equipment)

#### 6.2.2.2. Treatment Phase in repeated treatment courses

##### Visit 1 – day 1

Visit 1 – day 1, day of BI 6727 administration

- patient eligibility (in- and exclusion criteria)
- update of medical history

- physical examination including body weight, height, vital signs (blood pressure, pulse rate). Data from last visit of preceding course may be used in case examinations were done within the past 4 weeks.
- ECOG performance score
- laboratory examination including safety lab parameters (haematology including differential, biochemistry, coagulation parameters). Data from last visit of preceding course may be used in case examinations were done within the past 4 weeks.
- urine dipstick. Data from last visit of preceding course may be used in case examinations were done within the past 4 weeks.
- pregnancy test in women of childbearing potential
- changes in concomitant therapies
- occurrence of adverse events (AEs) since last visit

immediately before administration of BI 6727:

- resting ECG (series of three consecutive ECGs in third treatment course using dedicated equipment) at -0:15 min
- vital signs (blood pressure, pulse rate)

following administration of BI 6727 (start of infusion: 0:00) (the infusion rate needs to be constant during the whole infusion, deviations need to be documented in the eCRF. Duration (start and stop time of infusion) and actual dose administered need to be documented):

- resting ECG (series of three consecutive ECGs using dedicated equipment directly after completion of BI 6727 infusion (1h 15 min)
- vital signs (blood pressure, pulse rate) at 20 ( $\pm$  5 minutes), 65 ( $\pm$  10 minutes), 120 (2 hours;  $\pm$  30 minutes) and 240 minutes (4 hours;  $\pm$  30 minutes) after start of infusion
- Pharmacokinetic blood sampling: obtain blood samples 1:00 h (immediately prior to end of infusion of BI 6727) after start of infusion of BI 6727 (refer section 10.3 for sample handling). Blood samples have to be taken in the opposite arm of the infusion arm. For patients having central venous access, BI 6727 may be administered using this device and PK samples obtained from either forearm. The date and time of blood sampling must be recorded in the eCRF.
- adverse events occurring during and after infusion
- changes in concomitant therapy

Visit 2 – day 2

- vital signs (blood pressure, pulse rate)
- Pharmacokinetic blood sampling: obtain blood sample 24:00 h after start of infusion of BI 6727 (refer section 10.3 for sample handling). The date and time of blood sampling must be recorded in the eCRF.
- adverse events
- changes in concomitant therapy
- safety lab including haematology, biochemistry, coagulation parameters
- urine dipstick

Visit 3 - day 8 ( $\pm$  1) and Visit 4 - day 15 ( $\pm$  1)

- vital signs (blood pressure, pulse rate)
- adverse events
- changes in concomitant therapy
- safety lab including haematology, biochemistry
- Pharmacokinetic blood sampling: obtain blood sample at visit 3 (planned time: 168:00 hours after start of infusion of BI 6727) and at visit 4 (planned time: 336:00 hours after start of infusion of BI 6727), respectively (refer section 10.3 for sample handling). The date and time of blood sampling must be recorded in the eCRF.

Visit 5 – day 22 ( $\pm$  2)

- vital signs (blood pressure, pulse rate)
- ECOG performance score
- adverse events
- changes in concomitant therapy
- safety lab including haematology, biochemistry, coagulation parameters
- tumour assessment at the end of every other course:
  - MRI or CT if in accordance with RECIST or otherwise clinically indicated
- Endosonography or sonography optional

- resting ECG (series of three consecutive ECGs using dedicated equipment) in third course of treatment

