## FLOW CHART: REPEATED TREATMENT COURSES

Study Periods	Repeated treatment courses					EOT f	FU
	1	2	3	4	5		
Visit	1	2	3	4	5		
Day	1	2	8	15	22		
(day range)			(±1)	(±1)	(±2)		
Physical Examination	x g					x	x b
ECOG performance score	x					x	x
Pregnancy test	x						
MRI, CT a					x a		x
EUS, US (optional)					x		x
Body weight	x					x	
ECG	x k				x		x b
Infusion BI 6727	x						
Vital Signs	x	x	x	x	x	x	
Safety lab parameters	x g	x	x	x	x		x b
Urine examination	x g	x				x	
Pharmacokinetics (plasma)	x c	x c	x c	x c			
Adverse Events	x d	x	x	x	x	x	x e
Concomitant Therapy	x d	x	x	x	x		
Tumour assessment a					x a		x
Conclusion of Subject Participation						x	

a according to RECIST guidelines. Imaging and assessment are required at the end of every other treatment course.b optionalc for time schedule of pharmacokinetic sampling refer to table (Appendix 10.2), plasma samples have to be drawn from the opposite arm of the infusion. Intensive PK blood sampling performed in Course 1 only; for repeated courses PK blood sampling performed at the end of infusion (1:00h) after 24:00h, 168:00h and after 336:00h (Appendix 10.2).d update onlye if not yet recovered at the end of the previous course and in case of new adverse events if drug relatedf end of treatment; investigations which have to be performed at the last visit (when a patient discontinues the study)g data from last visit of previous course (day 22 ± 2) may be used in case examinations were done within the past four weeks

FU= follow up visit until progression, lost to follow up or treatment with another anti-cancer drug

k before administration and directly after completion of infusion of course 3 in eligible patients, further analyses in case of changes during prior courses

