### 3.3.3 Retreatment criteria

Patients with a clinical benefit after a course of BI 6727 (clinical response, absence of progression or symptom improvement) and who have recovered from any clinically relevant drug-related AE are eligible for a further treatment course. In case of symptom improvement despite disease progression a repeated course may be allowed in agreement between the clinical monitor and the investigator.

Patients experiencing DLT are eligible for further treatment courses with BI 6727 at one dose tier below as soon as recovery from drug related toxicities allows further treatment. Patients eligible for a further (repeat) treatment course will not start treatment before 22 ( $\pm$  2) days after start of the previous course. If an interruption of more than 6 weeks as counted from the start of the previous treatment course is necessary, the patient must be removed from this trial.

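### With an on-schedule last visit, the four-week lab reuse rule never binds before the six-week retreatment limit, so a delayed repeat course may start on haematology and biochemistry 19 to 23 days old

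*Protocol*

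**What the plan says.** Protocol 6.2.2.2 (Visit 1, day 1) lists haematology with differential, biochemistry and coagulation for each repeat course, then allows substitution: "biochemistry, coagulation parameters). Data from last visit of preceding course may be used in case examinations were done within the past 4 weeks". Footnote g of the flow chart for repeated courses, attached to the safety lab row, gives the same permission: "data from last visit of previous course (day 22 ± 2) may be used in case examinations were done within the past four weeks".

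The timing of the next course is set in Protocol 3.3.3. The earliest start is given as "Patients eligible for a further (repeat) treatment course will not start treatment before 22" (± 2) days after the previous start. The latest follows from the removal rule: "If an interruption of more than 6 weeks as counted from the start of the previous treatment course is necessary", the patient leaves the trial. Section 3.3.3 also limits retreatment to patients with clinical benefit "who have recovered from any clinically relevant drug-related AE are eligible for a further treatment course".

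On the same day 1, section 6.2.2.2 repeats the in- and exclusion criteria and lists "occurrence of adverse events (AEs) since last visit", ECOG score, concomitant therapy and pre-infusion vital signs. Section 5.2.5 times coagulation tests "at day 1 before start of infusion and at day 2". It leaves extra sampling in case of toxicity to the investigator's discretion.

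**The concern.** A maximum sample age is meant to stop dosing on outdated values. Here a second limit, on the treatment interval, always acts first, so for an on-schedule last visit the age limit has no effect. No visit is scheduled between day 22 and the next day 1.

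Exclusion criteria 6 to 10 are numerical limits on neutrophils, platelets, bilirubin, AST/ALT and creatinine, and SAP Table 6.2: 1 (A1.2) codes them as safety criteria. A delayed patient can pass them on values about three weeks old. A silent change in these values would not show in an adverse event review, ECOG score or vital signs, and coagulation tests do not measure them. If no extra sample is taken, the change would first be seen on day 2, after the infusion.

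The trial is first in human, and bone marrow is a main target organ in the animal studies (Protocol 1.2). Course 1 also lists haematology and biochemistry immediately before the infusion, with no reuse clause (6.2.2.1, Visit 2).

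**Working it through.** The plan states no figure of its own on this point, so there is none to reproduce. The check is day arithmetic.

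**Inputs**
- Reuse limit: 4 weeks = 28 days (6.2.2.2; footnote g).
- Last visit of a course, with labs: day v = 20, 22 or 24 (day 22 ± 2).
- Latest start: 6 weeks = 42 days after day 1 (3.3.3), so 1 + 42 = day 43.
- Undelayed start: 22 ± 2 days after day 1 (3.3.3), so 1 + 20 = day 21 to 1 + 24 = day 25.

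**Does the 28-day limit bind by day 43?**

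| Last visit v | Sample age at day 43 (43 − v) | Last reuse day (v + 28) | First day refused (v + 29) | Days after day 43 |
|---|---|---|---|---|
| 20 | 23 | 48 | 49 | 6 |
| 22 | 21 | 50 | 51 | 8 |
| 24 | 19 | 52 | 53 | 10 |

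It does not, for any on-schedule visit day. If day 1 is counted as the first of the 42 days, the latest start is day 42 and the ages are 22, 20 and 18 days; the conclusion is the same.

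**Undelayed patients.** The oldest on-schedule sample is 25 − 20 = 5 days.

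**Delayed patients.** Delayed start days run from 26 to 43, which is 43 − 26 + 1 = 18 days. The current rule refuses the sample on 0 of 18. A 7-day limit would first refuse it on day v + 8 = 28, 30 or 32:
- day 20 visit: 43 − 28 + 1 = 16 of 18
- day 22 visit: 43 − 30 + 1 = 14 of 18
- day 24 visit: 43 − 32 + 1 = 12 of 18

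**Which limits would work.** The limit must be at least 5 days to spare every undelayed on-schedule patient. It must be at most 18 days to bind at day 43 for every on-schedule visit, since the youngest sample is then 19 days old. With a day 22 visit, 14 days binds from day 37 (7 of 18) and 18 days only from day 41 (3 of 18).

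**Two edge cases**
- If day 22 is missed and the last sample is from day 14, it is 29 days old on day 43 and the limit binds on that day. Section 6.2.2.2 does not name the day of the last visit, but footnote g ties reuse to day 22 ± 2.
- SAP item C2.3 speaks of delaying a course by more than six weeks. Counted from day 22, that would be 22 + 42 = day 64. The protocol counts explicitly from the start of the previous course, so day 43 is used here.

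**The case against.** Reuse is optional: fresh labs are the listed default on day 1. The same visit repeats the eligibility check, including serious illness and active infection (exclusion criteria 1 and 3), so intercurrent illness is partly screened for. The contrast with course 1 has limits too. Screening may fall on day -14 and use labs up to two weeks older, so screening values can be about 14 + 14 = 28 days old at the first dose. No text there requires the day 1 results to be read before the infusion. The documents set no standard for 7 days, and a limit that is overtaken by another limit is not in itself an error.

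Most of this stands, and it keeps the point minor. It does not close the gap: no rule requires a fresh neutrophil, platelet, liver or creatinine value before a delayed dose, whereas course 1 does add a day 1 sample.

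A reader might infer three stronger things that the documents do not support:
- **That the dose is given on an unmeasured baseline.** The values were measured; they are old. The SAP baseline precedes the first administration in the first course (SAP 6.7), so no analysis baseline changes.
- **That patients with unresolved laboratory toxicity may be redosed on old labs.** Section 3.3.3 requires recovery, SAP item C2.2 lists continuing without it as a violation, and an abnormal day 22 value cannot show recovery.
- **That the MTD is compromised.** It is defined on first-course DLT (Protocol 5.2.1), which this rule does not touch. Later-course toxicity is considered in confirming it, but nothing in the documents shows an effect of sample age on that judgement.

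**Conclusion.** The point holds as a minor safety gap. With an on-schedule last visit, the four-week limit has no effect, and a delayed repeat course may start on haematology and biochemistry that are 19 to 23 days old at day 43.

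The affected group is narrow: patients delayed for a reason other than laboratory toxicity, with acceptable day 22 values, for whom the investigator chooses reuse. They have had no drug since the previous infusion, so the residual risk is mainly change from the cancer or another illness. A late marrow effect is less likely: neutropenia with the related inhibitor BI 2536 was quickly reversible (Protocol 1.4), although BI 6727 itself had no clinical data.

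The documents give neither the number of delayed courses nor how often values change in the interval, so the number of patients affected cannot be estimated. The conclusion rests on the protocol of 3 October 2005. The SAP names three later amendments, which are not available and may have changed this wording.

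**What to change.** In 6.2.2.2 and footnote g, for safety labs only, shorten the reuse limit from four weeks to 7 days. When the last sample is older than that, require fresh haematology with differential and biochemistry, with the results reviewed against exclusion criteria 6 to 10 before the infusion. The review must be stated, because a draw alone would not inform the dosing decision. Footnote g also covers physical examination and urine dipstick, so the safety lab row needs its own footnote.

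Seven days is a proposal within the workable range of 5 to 18 days; a shorter limit covers more of the delayed start days.

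The cost is a wording change, plus at most one routine blood draw, already listed for the visit, and a short wait for results per delayed course. Undelayed on-schedule patients need no extra draw.
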